- *Randomization:* During the first outpatient study visit, participants will meet with a study counselor to discuss randomization assignment. They will be provided with 4 days of food and will again be instructed to eat only the foods provided, consume no additional foods, maintain their current levels of physical activity, and to keep track on a self-monitoring food record form. Additionally, they will be instructed on how to use the smart-phone system
 - Heart-Healthy Dietary Prescriptions:
 - Both the lean and obese WMEN groups will continue to eat the same number of calories that were calculated for them during the baseline weight maintenance period

- The obese UF group will be assigned a diet of 35% of the calculated energy needs
- *Weight and BP*: obtained at each visit
- *Meal pick-up*: meals will be prepared by the metabolic kitchen and picked up on a twice weekly basis
- *Meeting with Study Counselor*: Participants will meet 1x/week with a study counselor to review food records and dietary adherence. The counselor will rate the participants adherence and participant will rate his/her adherence to the dietary prescription and to behavioral aspects on a 5- point Likert Scale (0 = low; 5 = high). Counselors will also obtain a rating of subjective hunger over the last week on the same Likert Scale (0 = low; 5 = high) and assess change in physical activity. Sessions will last 15-30 minutes.
- *Assessment of Adherence*: Subjects will complete additional assessments of adherence:
 - 24-hour recall: this will be conducted by a member of the study staff other than the primary counselor to avoid bias
 - Computerized confessional: participants will complete a computerized battery of questions that will include a 24-hour recall with prompts to encourage recall of various foods possibly consumed at various times during the day. Questions about other weight and eating behaviors will be included. Data from this procedure will enable us to compare with the in-person interview version of the 24-h recall and assess reliability

Outpatient Adherence Contacts:

- 24-h recall by phone: a member of the study staff will call at a random time, 1x/week to conduct a 24-h food recall

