The design of this study will allow us to look at differences in levels of adherence to a heart-healthy dietary prescription in lean vs. obese individuals. We will also be able to compare adherence levels in obese individuals who are being fed a WMEN diet compared to an UF diet. Additionally, we will measure predictors of adherence and the relationship between adherence and weight loss.

Data Analysis:

Measuring Adherence: (see Appendix B): for all measures, adherence will be examined as a binary variable (adherent versus non-adherent). Each measure will be awarded 0 points if non-adherent and 1 point if adherent.

1. Attendance: two sessions per week: (adherent = attended; non-adherent = not attended; 12 possible total points over the study).
 - a. counseling
 - b. food pick-up
2. Food Diaries: volunteers will turn in diaries during their weekly counseling visit. For each weekly diary there will be three scores (18 possible total points over the study):
 - a. *Completion of records*: adherent = completed diary; non-adherent = missing or incomplete diaries
 - b. *Dietary Adherence to Foods provided*: adherent = consumed all; non-adherent = did not consume all
 - c. *Adherence to Additional Foods*: adherent = did not consume any; non-adherent = consumed additional foods
3. 24-hour recall in-person interview: once per week on day of counseling session. For each session there will be three scores (18 possible total points over the study):
 - a. *Completion of interview*: adherent = completed interview; non-adherent = did not complete interview
 - b. *Dietary Adherence to Foods provided*: adherent = consumed all; non-adherent = did not consume all
 - c. *Adherence to Additional Foods*: adherent = did not consume any; non-adherent = consumed additional foods

4. 24-hour recall using computerized confessional: once per week on day of counseling session. For each session there will be three scores (18 possible total points over the study):
 - a. *Completion of records*: adherent = completed interview; non-adherent = did not complete interview
 - b. *Dietary Adherence to Foods provided*: adherent = consumed all; non-adherent = did not consume all
 - c. *Adherence to Additional Foods*: adherent = did not consume any; non-adherent = consumed additional foods
5. 24-hour recall (telephone): once per week. For each phone session there will be three scores (18 possible total points)

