 - a. *Completion of recall*: adherent = completed recall; non-adherent = did not complete recall
 - b. *Dietary Adherence to Foods provided*: adherent = consumed all; non-adherent = did not consume all
 - c. *Adherence to Additional Foods*: adherent = did not consume any; non-adherent = consumed additional foods
6. EMA recordings: there will be two contacts per day. For each contact there will be three adherence scores. To avoid having EMA be more heavily weighted in the total score, the total weekly score will be divided by 7 to obtain an average weekly EMA score (42 possible total points per week; 6 possible total average points):

- a. *Completion of recording*: adherent = completed recording; non-adherent = did not complete recording. We will define incomplete or missing entries as non-adherent for that day.
 - b. *Dietary Adherence to Foods provided*: adherent = consumed all; non-adherent = did not consume all
 - c. *Adherence to Additional Foods*: adherent = did not consume any; non-adherent = consumed additional foods
7. Additional Non-Intervention Related Adherence Measure (once per week. For each rating there will be 1 score (6 possible total points over the study): We will also track the arrival time for weekly counseling session as a measure of adherence that is not directly related to the study intervention. Appointment adherence will be scored as the arrival within 5 minutes of the scheduled time and actual arrival time will be documented as a continuous measure of adherence. This measurement will allow us to examine the relationship between adherence to the dietary protocol and adherence to "other" factors (e.g. punctuality) and it will be included in the total adherence score.
- a. Appointment adherence: adherent = arrived within 5 minutes of scheduled appointment; non-adherent = did not arrive within 5 minutes of scheduled appointment

Adherence Score: The above variables will be totaled up to calculate a total adherence score out of a possible 21 points during each week. A percent (%) adherence score will also be calculated by dividing the total score by the number of variables assessed (21) and multiplying by 100 ($[(\text{total}/21)*100]$).

Statistical Analysis:

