For our primary hypothesis, a one-way ANOVA will be performed with total adherence score as the dependent variable and group status (lean WMEN, obese WMEN, obese UF) as the independent variable. In addition, linear regression models adjusted for covariates including age, sex, race, socioeconomic status (SES) and baseline weight or percent body fat will also be used to examine the relationship of adherence and behavioral factors. Correlations between adherence scores, behavioral test scores and weight, fat mass and fat free mass loss will be calculated. Pearson's r will be calculated for data that are normally distributed and Spearman's correlation will be used if the distributions are non-normal. This will be an intention to treat study such that everyone who completes the run-in phase will be included in the final analysis. Missing data will be completed using a multiple imputation method utilizing the SAS procedures, PROC MI and MIANALYZE. This method introduces variability into the imputed values to reduce the risk of a type 1 error. All tests will have a 2-sided Type I error of $p = 0.05$.

Power Calculation:

Sample size calculations are based on the number of individuals needed to demonstrate a significant difference in adherence scores over the 6-week intervention period between the 3 diet groups (lean WMEN, obese WMEN, obese UF).

We based our expected percent adherence score on a recent paper by Williamson et al (26) who observed 52% adherence in a group of obese dieters. Our maximum possible adherence score is 21 per week. To account for the increased adherence we expect to see because food is being provided in the study, we have increased the proposed adherence from the 52%

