8.3.a Radiation exposure due to DXA: The DXA scans will take place on the GE Lunar iDXA machine. The radiation exposure for a 188 mA scan may be as much as 1 mrem as indicated by a January 2014 internal radiation exposure review. According to the manufacturer, the medium and fast scan speeds are likely to result in one-half the radiation exposure of the slow scan speed. A typical radiation dosage from this procedure is equivalent to 1.22 days (iDXA) of exposure to natural background sources, such as the sun and outer space, or radioactive materials found naturally within the earth's air and soil. For subjects who move excessively during the scans, a complete or partial repeat of the scan procedure may be necessary. Thus, subjects could receive a maximum of 2 mrem (iDXA, 2.5 days of exposure) if the slow scanning mode is used each time. Participants in this study will undergo 2 DXA scans over the study period therefore the maximum amount of radiation they will receive in the first year could be as high as 4 mrem (iDXA, 5 days of exposure). This exposure increases the percent cancer risk from 25 percent to 25.00016 (iDXA). This is well within the NIH Phoenix Radiation Safety Guidelines for research subjects of 3,000 mrem in a 13-week period and 5,000 mrem per year. A urine pregnancy test will be performed in all females who are able to become pregnant prior to each DXA scan.

8.3.e Dietary Intervention: The side-effects of consuming a pre-selected diet are minimal and might include boredom, lack of desire to eat the prescribed foods and/or increased feelings of hunger.

8.3.e Questionnaires and computer performance tests: There are no known risks associated with completing any of these questionnaires. However, some of the questions may be of a highly personal nature; thus, subjects will be informed that they do not have to respond to all the questions if they choose not to do so. If this is the case, notations to that effect will be noted in the patient's record.

8.3.f Urine Drug Screen: Results of this test will be used only to determine study eligibility. If the result is positive, patients will be confidentially informed of the results and a recommendation for follow-up will be made with their primary physician.

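### The adherence total gives finishing the supplied food and eating nothing else equal weight; if the underfed diet shifts them in opposite directions, the total can hide a difference in off-plan eating, so both components should be compared as supportive analyses

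*Combined protocol and SAP*

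**What the plan says.** Under Measuring Adherence in section 6, every item is binary: "Each measure will be awarded 0 points if non-adherent and 1 point if adherent". The weekly diary, the in-person recall, the computerized confessional, the telephone recall and the two daily smartphone (EMA) contacts each carry three items. One is for completing the record. One is for the food supplied: "adherent = consumed all; non-adherent = did not consume all". One is for other food: "adherent = did not consume any; non-adherent = consumed additional foods". For EMA, "the total weekly score will be divided by 7 to obtain an average weekly EMA score".

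The Adherence Score paragraph then sums everything: "The above variables will be totaled up to calculate a total adherence score out of a possible 21 points during each week". The percent score is the same total rescaled. Under Statistical Analysis, for the primary hypothesis "a one-way ANOVA will be performed with total adherence score as the dependent variable" and the three groups as the factor. No group comparison of the food items is specified, and no reason is given for weighting them equally.

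On the diets, the two WMEN groups stay on their baseline calories, and "The obese UF group will be assigned a diet of 35% of the calculated energy needs". The opening summary describes the UF diet differently, as a reduction of 35% from daily needs. Section 8.3.e lists possible side effects of a pre-selected diet, among them "lack of desire to eat the prescribed foods and/or increased feelings of hunger", without tying either to an arm.

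**The concern.** Obese WMEN versus obese UF is one of the two comparisons in the primary aim. What separates those arms is the quantity of food supplied, and quantity plausibly affects how hard each food item is to satisfy. A smaller ration may be easier to finish and harder not to supplement. If so, UF participants would gain on one item type and lose on the other, and the total would show only the net.

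A small or null UF difference in the total could then be read as adherence not depending on the prescription, while the arms departed from it in different ways. Secondary hypothesis 1 is touched too: a UF participant who leaves supplied food loses points while eating less.

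**Working it through.** **Weights (Measuring Adherence; score sheet).**
- Foods provided: diary 1 + interview 1 + computer 1 + telephone 1 + EMA (2 × 7)/7 = 2, which makes 6 per week.
- Additional foods: the same sources, 6 per week.
- Process: completion 6 + attendance 2 + punctuality 1 = 9.
- Sum: 6 + 6 + 9 = 21, as stated.

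**The plan's own example (score sheet, week 1).**
- Finish: 0 + 1 + 1 + 1 + (6 + 5)/7 = 4.57.
- No-extra: 0 + 0 + 0 + 0 + (4 + 2)/7 = 0.86.
- Process: attendance 2 + completion (0 + 1 + 1 + 1 + 12/7) + punctuality 1 = 7.71.
- Total: 13.14, against 13.1 (62%) on the sheet.

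Swapping the two food components leaves 13.14. A person who finishes most of the food but often eats other food scores the same as one who leaves food but rarely eats anything else.

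**Stated power, reproduced.** Inputs from Power Calculation: means 19/16/13, SD 6, 20 per group, alpha 0.05. The squared deviations from the mean of 16 sum to 9 + 0 + 9 = 18. The noncentrality is 20 × 18/36 = 10 on 2 and 57 degrees of freedom, which gives power 0.793, as stated. The second scenario (20/16.5/13) gives 0.906, as stated.

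**Offset identity.** With process points equal between the obese arms:

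UF − WMEN = 6 × (gain in finish rate − loss in no-extra rate).

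Equal shifts give zero. For a 3-point gap, the no-extra loss must exceed the finish gain by 3/6 = 50 percentage points.

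**Limit on the offset.** The finish rate cannot exceed 100%. Obese WMEN is planned at 16/21.
- If every item runs at 16/21 = 76%, the finish rate can rise by 24 points, an offset of at most 6 × 5/21 = 1.43.
- If all 9 process points are earned and the food items are equal, they run at 7/12 = 58%. The finish rate can rise by 42 points, an offset of at most 6 × 5/12 = 2.5.

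Under these two assumptions, a 3-point loss would still show as 3 − 1.43 = 1.57 or 3 − 2.5 = 0.5 points.

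**Illustration (assumed shifts; lean 19, obese WMEN 16, SD 6, 20 per group).** The pairwise test is not in the plan and is shown for scale.

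| No-extra loss (points) | Finish gain (points) | UF mean | Omnibus power | UF vs obese WMEN, total |
|---|---|---|---|---|
| 3 | 0 | 13 | 0.793 | 0.34 |
| 3 | 0.75 | 13.75 | 0.68 | 0.21 |
| 3 | 1.5 | 14.5 | 0.55 | 0.12 |
| 1.5 | 1.5 | 16 | 0.34 | 0.05 (alpha) |

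In the last row the omnibus power comes only from lean versus obese. The no-extra sub-score alone would detect that same 1.5-point loss with power 0.77, 0.49 or 0.34, at assumed sub-score SDs of 1.71 (6 × 6/21), 2.4 or 3.0.

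**The case against.** The strongest reply is that the opposite direction is not documented, and that is correct. Section 8.3.e is a generic list. It does not assign hunger to UF or lack of desire to WMEN. Maintenance rations are set to calculated needs and adjusted if weight changes in the baseline week, so nothing shows that they are hard to finish. The items could also fail together, since someone who eats other food may leave the supplied food.

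Second, the planned UF mean of 13 is 62% of the whole 21-point score, so it is already a net figure. A reader might infer from the table that the true power is 0.68 to 0.55 and that the stated 0.793 is wrong. The documents do not support that. 0.793 is correct for its inputs, and the lower figures follow only if the whole 3-point gap is taken as a loss on the no-extra items before any offset. The pairwise starting value of 0.34 reflects sample size, not item weighting.

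Third, the total fits the protocol's definition of adherence as following instructions, and eating only the supplied food is part of those instructions. An equal total is a fair statement about overall adherence so defined. This supports keeping the total, but it does not make the total informative about which behaviour differed.

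Fourth, sub-scores mix behaviour with missing records. The score sheet gives the uncompleted diary 0 on all three items, and missing EMA entries count as non-adherent. Missingness therefore moves both components down together. This stands, and the fix has to deal with it.

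Finally, the items are recorded separately, so components could be examined later. However, a component result reported after a null total would be post hoc.

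**Conclusion.** The point holds as a low-cost improvement, not as an error in the primary analysis. It is established that the two food item types carry 6 of 21 points each, that they are summed, and that only the total is compared between groups. It is plausible but undocumented that the amount of food supplied moves them in opposite directions. If it does, a difference in off-plan eating is diluted, and for equal shifts it is cancelled. Under the two ceiling assumptions above, full cancellation is limited to losses of about 1.4 to 2.5 points per week. The power figures are illustrations on assumed shifts and do not correct the stated power. The issue concerns obese UF versus obese WMEN. Lean versus obese WMEN is not affected by this mechanism, because both groups are fed to maintenance.

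The two descriptions of the UF diet, 35% of needs and 35% below needs, contradict each other and must be reconciled. UF participants are supplied less under either wording, so the conflict bears on the size of any offset and not on its direction.

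**What to change.** Keep the 21-point total and the one-way ANOVA as primary. Add to Statistical Analysis:

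- The same three-group comparison, with the obese UF versus obese WMEN contrast, is run for the foods-provided sub-score and for the additional-foods sub-score (0–6 per week each). Both are supportive, with no claim of confirmatory significance.
- Each component is also shown as a proportion of completed records, beside the sub-score, so that missing records scored as non-adherent do not drive both. Completion may itself differ by arm, so the proportion is read together with completion rates and does not replace the sub-score.
- The total is interpreted alongside the components. If they differ between the obese arms in opposite directions, that is reported, and not only an absence of difference in adherence.

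Separately, reconcile the two descriptions of the UF diet.

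The cost is one paragraph and two further runs of the same model on items already on the score sheet, with no new data, visits or participants. The downside is two more supportive comparisons to report.

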Personality is another factor significantly influencing health. The most common relationship between these variables is based on the Five Factor Model dimensions (FFM; (20)) - Neuroticism, Extraversion, Openness, Agreeableness and Conscientiousness, which are empirically derived clusters that capture the major axes of psychological and behavioral variation in humans (21;22). FFM factors have been linked with many health-related behaviors and outcomes, including medication non-adherence. One recent study found that neuroticism was the second strongest predictor of non-adherence to CPAP treatment for obstructive sleep apnea (23). Previous studies have shown that medication non-adherence (24) as well as emotional and external eating behaviors (25) were most frequently associated with lower levels of

Conscientiousness and higher levels of Neuroticism. However, no study to date has measured FFM with weight loss and/or dietary adherence.

Successful weight management appears to require adherence across a wide variety of behaviors yet measuring adherence poses a significant problem. While objective behavioral measures are superior to subjective self-report measures, objective measures are often difficult to obtain. Both early behavioral (e.g. attendance) and self-reported dietary adherence were predictors of changes in body weight, waist circumference and body fat, but for dietary adherence the magnitude of the effect was smaller (26). It is widely accepted that adherence to weight management strategies is critical for successful weight loss and for long-term maintenance (1). However, it is not clear whether problems with adherence occur more frequently with diets to promote weight loss versus weight maintenance, any diet prescription, and whether increased adiposity might in itself predispose to more difficulty with dietary and behavioral adherence. Our study aims to address these questions.

Summary:

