Adherence is essential for initial weight loss and long-term weight maintenance. It is unclear whether adherence to dietary protocols differs between lean and obese individuals and whether non-adherence is specific to weight loss intervention diets (compared to weight maintenance diets). Several predictors of adherence to medical treatments have been described, including associations with memory, problem solving, neuropsychological factors, personality traits and levels of motivation. To understand how adherence may differ by adiposity and diet, we will examine differences in dietary adherence between lean and obese individuals and within the obese group between those prescribed a heart-healthy weight maintenance versus reduced calorie

diet. We will also examine predictors of adherence and the relationship between dietary adherence and weight loss.

B. AIMS

The primary goal of the current study is to determine whether or not there are differences in dietary adherence between lean and obese individuals and between two groups of obese individuals assigned different heart-healthy dietary prescriptions (weight maintaining diet [WMEN] vs. underfeeding [UF]). Thus 3 groups will be compared:

1. Lean WMEN
2. Obese WMEN
3. Obese UF

The secondary aim is to:

1. Examine predictors of adherence in general (e.g. motivation, self-efficacy, social support, personality traits, stress, neuropsychological/cognitive factors)

C. HYPOTHESES

The primary hypothesis for the study is that:

1. Adherence to a heart-healthy dietary intervention will be greatest in the lean WMEN group, followed by the WMEN obese group, and subsequently lowest in the UF obese group

The secondary hypotheses are that:

1. Within the UF group, individuals with higher adherence scores will lose more weight than those with lower scores

2. Poor performance on neuropsychological tests and problem solving questionnaires will be associated with decreased adherence across all groups
3. Higher levels of neuroticism will be associated with lower levels of dietary adherence in all 3 groups
4. Higher levels of motivation and self-efficacy will predict greater adherence

D. RESEARCH DESIGN & METHODS:

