Study Design: This is a study of lean and obese individuals undergoing a 6-week heart-healthy dietary intervention to examine dietary adherence. This design will allow us to determine whether or not levels of adherence are different between lean and obese individuals as well as between obese individuals receiving weight maintenance energy needs and those being underfed. Findings will also help us determine factors that influence dietary adherence.

1. Subjects and Recruitment: Non-diabetic individuals aged 18-70 years who are in good health and living in the greater Phoenix, AZ, metropolitan area are eligible to participate in this study. All subjects will be fully informed of the methods and risks of the study prior to giving written informed consent. Consent will be obtained by the principal investigator, co-investigators, study physicians or physician assistant, who will be well informed about the protocol and the intervention. Subjects will also be specifically advised that the results of testing for drug usage will be filed in the medical record and would, therefore, be available as part of this record. We do not plan or anticipate the enrollment of non-English speaking subjects; however they are not excluded from participation either. Should a non-English speaking subject be eligible for enrollment, IRB approval will be obtained for use of the short form consent

process in the absence of a fully translated consent document as outlined in SOP 12.9.1, under the provisions of 45 CFR 46.117(b)(2). IRB approval will be obtained according to IRB guidance prior to obtaining informed consent from the potential study participant/s.

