- Go/No Go Task (45): to examine inhibitory control. Subjects are required to press a key whenever a target stimulus is presented and to refrain from pressing the key when a non-target stimulus is presented
 - Meeting with study counselor: The counselor will review the weight-maintenance heart-healthy dietary prescription and provide the volunteer with 3 days of food. The volunteer will be instructed to eat only the foods provided, consume no additional foods, maintain their current levels of physical activity, and to keep track on a self-monitoring food record form.
 - Weight Maintenance Dietary Prescriptions:
 - Recent studies have found that using free prepared meals facilitated greater adherence (16) and weight loss compared with a control group (17). Therefore, because the primary aim of our study is to compare differences between lean and obese groups and WMEN versus UF diets (rather than investigate real-world learning), all food items will be provided by the CRU, primarily as prepackaged meals and snacks for the volunteers to take home (see Table 2 for sample menu).
 - All diets will have 20%, 30%, and 50% of daily calories provided as protein, fat and carbohydrate, respectively. They are designated as "heart-healthy" because they will be balanced diets, which are also low in cholesterol and saturated fat.
 - During the baseline week, all participants will be fed their weight maintaining energy needs (WMEN), equal to the number of calories calculated for each participant based on the WHO equation with an activity factor (1.3-1.5)(46;47), based on results from the PAR questionnaire.

- *Women:* 18 to 30 y: $EE = 13.3 \times \text{weight (kg)} + 344 \times \text{height (m)} + 35$
30 to 60 y: $EE = 8.7 \times \text{weight (kg)} - 25 \times \text{height (m)} + 865$
- *Men:* 18 to 30 y: $EE = 15.4 \times \text{weight (kg)} - 27 \times \text{height (m)} + 717$
30 to 60 y: $EE = 11.3 \times \text{weight (kg)} + 16 \times \text{height (m)} + 901$
- During the first week, and prior to randomization, all patients will come for 2 outpatient visits to be weighed
- If their weight changes by 2%, their caloric intake will be adjusted by 200 kcal accordingly

Baseline Visit 2:

1. Weight
2. Adjust calories by 2%, if needed

Outpatient Visits (6 weeks):

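### The primary hypothesis names two group comparisons and an order, but the plan tests it only with an overall F test, and the stated power does not apply to the adjacent-group comparisons

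*Combined protocol and SAP*

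**What the plan says.** Section B (Aims) sets the primary goal as "differences in dietary adherence between lean and obese individuals and between two groups of obese individuals assigned different heart-healthy dietary prescriptions". It then states that three groups are compared and lists lean WMEN, obese WMEN and obese UF separately. Section C gives an ordered primary hypothesis: "Adherence to a heart-healthy dietary intervention will be greatest in the lean WMEN group, followed by the WMEN obese group", with obese UF lowest. The same two comparisons recur in the Study Design paragraph of Section D, in the dietary prescription text ("the primary aim of our study is to compare differences between lean and obese groups and WMEN versus UF diets") and at the start of Section D.6 ("We will also be able to compare adherence levels in obese individuals who are being fed a WMEN diet compared to an UF diet").

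The Statistical Analysis part of Section D.6 assigns one test: "For our primary hypothesis, a one-way ANOVA will be performed with total adherence score as the dependent variable and group status". The covariate-adjusted regressions that follow are for adherence in relation to behavioral factors. Every test is two-sided at 0.05, and missing data are multiply imputed. No contrast, trend test, post hoc procedure or multiplicity rule appears.

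The Power Calculation assumes means of 13 (obese UF), 16 (obese WMEN) and 19 (lean WMEN), SD 6 and 20 per group, and reports power 0.793. A second scenario, 13 / 16.5 / 20, gives 0.906. Tables 3A and 3B label both as power for the overall F test.

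**The concern.** A significant overall F says that the three means are not all equal. It does not say whether adiposity, calorie restriction or both matter, or in which order the groups fall, and those are the questions in Sections B and C. Followed exactly, the plan stops short of its own primary hypothesis.

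The follow-up tests would then be chosen after the data are seen. That choice affects the error rate, because testing the two adjacent pairs at 0.05 each with no rule exceeds 5% familywise. A reader who takes 0.793 as the chance of answering the diet question would also misread a non-significant obese WMEN vs obese UF result as evidence that calorie restriction does not matter.

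**Working it through.** **Inputs.** Means 13 / 16 / 19 (always in the order UF / obese WMEN / lean), SD 6, 20 per group and two-sided 0.05, all from the Power Calculation and Table 3A. SDs of 5 and 4 are assumptions, used to show a range.

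**1. The plan's figures reproduce.** Overall F, df 2 and 57, noncentrality n × Σ(mean − grand mean)² / SD²:
- 13 / 16 / 19: 20 × (9 + 0 + 9) / 36 = 10, power 0.793.
- 13 / 16.5 / 20: 20 × (12.25 + 0 + 12.25) / 36 = 13.61, power 0.906.

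Both match the tables. (The sum of squares of 32 printed in the text is not the 18 that produces 0.793; that is a separate matter.)

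**2. The F test ignores order.** For 13 / 19 / 16, which contradicts the hypothesis, the sum of squares is again 18, the noncentrality 10 and the power 0.793.

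**3. Power of an adjacent comparison.** Noncentral t with the ANOVA error term (df 57) and noncentrality 3 / (SD × √(2/20)):

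| SD | Noncentrality | Power, 20 per group | Power, 25 per group (df 72) |
|---|---|---|---|
| 6 (plan) | 1.58 | 0.34 | 0.41 |
| 5 (assumed) | 1.90 | 0.46 | 0.55 |
| 4 (assumed) | 2.37 | 0.64 | 0.74 |

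The last column treats all 25 recruited per group as fully informative, an upper bound on what imputation could recover. Lean WMEN vs obese WMEN has the same 3-point gap and so the same power.

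**4. What a significant F leaves open** (simulation, at least 400,000 trials per scenario, means 13 / 16 / 19). Obese WMEN vs obese UF is non-significant in 58% / 50% / 35% of significant-F trials at SD 6 / 5 / 4. Both adjacent steps are significant in the predicted direction in 0.06 / 0.14 / 0.35 of all trials.

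**5. Familywise error, all means equal.** At least one of the two adjacent tests is significant in 9.0% of trials with no rule, 4.2% if both are gated on a significant F, and 4.6% with Holm.

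**6. What each rule costs.** Power for obese WMEN vs obese UF at SD 6, 20 per group:

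| Means | No rule | F gate | Holm |
|---|---|---|---|
| 13 / 16 / 19 | 0.34 | 0.335 | 0.259 |
| 13 / 16 / 16 | 0.34 | 0.260 | 0.245 |
| 13 / 16 / 14.5 | 0.34 | 0.235 | 0.252 |

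Under the gate, an adjacent 95% CI excludes zero with no claim allowed in 1.8% of trials at 13 / 16 / 19, about 9% at 13 / 16 / 16 and 4.8% with equal means.

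**7. A limit on the SD.** The weekly score runs from 0 to 21. For a score on that range with mean m, the SD cannot exceed √(m × (21 − m)). At mean 20 this is √20 = 4.47; at mean 19 it is √38 = 6.16. A common SD of 6 is therefore impossible in the 3.5-point scenario, and close to the limit for the lean group in the 3-point one.

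**The case against.** The strongest reply is that the ANOVA is a valid global test, that its power is computed correctly, and that the tables say plainly what the figure is. All of that stands. A reader might infer that the power calculation is wrong, or that the protocol promises 0.793 for a pairwise comparison. The documents support neither: they tie the sample size to a difference among three groups and never attach 0.793 or 0.906 to a pair.

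A reader might also infer that lean vs obese is hopelessly ambiguous, because it could mean lean vs both obese groups pooled (power 0.77 at a 4.5-point difference). That overstates it. The Aims list three separate groups, the hypothesis orders them, and the Introduction asks "whether increased adiposity might in itself predispose to more difficulty with dietary and behavioral adherence. Our study aims to address these questions". All this points to lean WMEN vs obese WMEN, so the sponsor need only confirm it. Obese WMEN vs obese UF is the same contrast on either reading.

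The bounded score also tells against SD 6, at least for the lean group, so 0.34 may understate the power. A range is therefore given. Even at SD 4 with 20 per group, adjacent power is 0.64.

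Post hoc tests after an ANOVA are routine, but none is named here, and the choice moves familywise error between 9.0% and about 4 to 5%.

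**Conclusion.** The point holds as an omission that should be fixed. The only test assigned to the primary hypothesis cannot establish the order or either named comparison, and the stated power does not carry over to the adjacent comparisons: about 0.34 against 0.793 at the plan's inputs, with 0.46 and 0.64 at assumed SDs of 5 and 4. These figures assume normal scores with a common SD, complete data and equal groups of 20.

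It does not follow that the ANOVA is invalid or that every comparison is weak: lean WMEN vs obese UF, a 6-point gap, has power 0.87. Nor is an F gate always the better remedy. Its advantage at 13 / 16 / 19 nearly vanishes if only calorie restriction matters (13 / 16 / 16), and reverses at 13 / 16 / 14.5.

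**What to change.** Keep the one-way ANOVA and add the following to Statistical Analysis in Section D.6:

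- Two contrasts from the same model test the primary aims: lean WMEN vs obese WMEN (sponsor to confirm this reading) and obese WMEN vs obese UF. Both are reported with 95% CIs.
- Familywise error is held at 0.05 by one rule chosen now: either both contrasts are tested only after a significant F, or Holm is applied over the two. With three groups either is valid.
- The rule is applied to the multiply imputed results. If the gate is chosen, say how the F test is pooled across imputations, and that when F is not significant the CIs are descriptive even if one excludes zero.
- The full ordering is claimed only if both contrasts are significant in the predicted direction.

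In the Power Calculation, label 0.793 and 0.906 as overall-F power and print the 3-point contrast power beside them: 0.34 / 0.46 / 0.64 at SD 6 / 5 / 4, with 5 and 4 marked as assumptions. Do not add a contrast figure for the 3.5-point scenario at SD 6 (it would be 0.44), because that SD cannot occur with a mean of 20.

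The cost is wording, a less favourable stated power for the individual comparisons, and the power loss shown for the chosen rule. No participants or data are added. The shortfall is disclosed, not cured: 80% power per adjacent contrast at 3 points would need about 64, 45 or 29 per group at SD 6, 5 or 4, before any familywise adjustment.
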